### **Research samples:**

- 1) Blood: All blood specimens are collected for the PK, neutralization, and IgG assays. Immediately prior to mAb administration, at the end-of-infusion, weekly up to week 4, monthly up to week 12, and at week 24 after mAb administration, blood will be collected by venipuncture (10-20 mL per blood draw). Blood drawn from a central venous catheter is permitted. Blood from venipuncture or a central venous catheter will be collected by inpatient nursing, outpatient nursing, phlebotomy, or the study team. If the participant is unable to return to the clinic or hospital for their last blood draw (week 24), we may provide a kit including blood collection tubes so a blood draw can be performed at the participant's local phlebotomy clinic or lab and shipped back to the study site. At week 12, and monthly thereafter to the last blood draw (week 24), blood will be by venous blood draw and self-collected using a TASSO-SST or TASSO+ device. The Tasso™ (Tasso Inc., Seattle WA) device is optimized for needle-free self-collection of blood at home. The TASSO-SST and TASSO+ devices can collect up to 300 µL and 600 µL, respectively, of whole blood from capillaries that can be spun down to serum. For each TASSO time-point, blood will be collected in either two TASSO-SST devices or one TASSO+ device. Each participant will be provided with a backup TASSO device for each TASSO collection time-point in case of device failure (expected 15% failure rate). We have experience using this technology with ongoing COVID-19 antibody testing studies at FHCRC (249 subjects and 2,289 devices). According to the manufacturer, the device has been used in over 5000 subjects since 2004 without any known severe events. The risk for participants is minimal and comparable to the procedures (lancing) for monitoring blood sugar levels. Additional blood may also be collected off-schedule as needed based on reporting of respiratory symptoms (one or more nose or chest symptoms) on the weekly questionnaire (if a specimen is not already scheduled to be collected within a week) for PK, neutralization, and IgG assays. Additional blood samples may also be requested due to inadequate collection or issues related to mail service delivery. Samples will be processed and stored at -20°C or -70°C until use, as appropriate.

2) Nasal specimens: Sample collection kits will be provided for the collection, handling, and shipping of samples to the [name] laboratory. Participants will self-collect mid-nasal swabs using a foam swab at the same time-points as blood draws. We have compared the performance of self-collected mid-nasal swabs to nasopharyngeal swabs collected by a medical professional and have observed high concordance (Table 2). In addition, we have found high concordance in the use of the mid-nasal foam swabs with nasal washes and flocked swabs for the detection of respiratory viruses (27, 28). Additional nasal swabs may also be collected off-schedule as needed based on reporting of respiratory symptoms (one or more nose or chest symptoms) on the weekly questionnaire within 48 hours of symptom onset, up to week 36. If positive for SARS-CoV-2, weekly nasal swabs will be obtained longitudinally for SARS-CoV-2 PCR until negative or until week 36. Samples will be processed and stored at -20°C or -70°C until use, as appropriate, for SARS-CoV-2 PCR testing and also potentially for antibody testing.

		Nasopharyngeal	
		Positive	Negative
Self-collected	Positive	36	0
	Negative	0	117
	Inconclusive	1	1

Samples collected in the inpatient unit or outpatient infusion center will be picked up by a member of the study team and brought to the [name] Lab on the same day of collection. Samples collected at home will be shipped overnight via FedEx to the [name] Lab.

### Medical records:

Medical records from the University of Washington, outside health care providers, and databases maintained by the Fred Hutchinson Cancer Center will be reviewed for data such as subjects' demographics, underlying malignancy, treatment, and medical history with a focus on HCT related treatment and disease response.

- At screening, these include review of standard pre-transplant medical history and labs to assess inclusion/exclusion criteria:
  - Age
  - Underlying disease
  - HCT planned type and date
  - History of prior transplants

- History of COVID-19, positive PCR of a respiratory specimen for SARS-CoV-2 as long as it is not within four weeks from conditioning, or seropositivity for SARS-CoV-2
  - History of SARS-CoV-2 infection or vaccination of the donor
  - Ability to provide informed consent
  - Prior administration of IVIG
  - Pregnancy test results
  - Previous known allergies to any component of VIR-7831
  - Previous anaphylaxis or severe hypersensitivity reaction, including angioedema, to a mAb
  - Participation in other clinical studies that preclude the use of other investigational compounds
- On the day of infusion, at the end-of-infusion, weekly to week 4, and monthly to week 24, these include review of the medical history with regards to underlying disease, medications, history of infections, history of vaccinations, and presence/severity of GVHD. In addition, standard post-transplant laboratory testing which are collected as follows from Day 0 to +100 post-transplant and as clinically indicated thereafter will be reviewed, including:
  - CBC daily until granulocytes > 500 cells/mm^3 and platelets > 20,000 cells/mm^3, then a CBC a minimum of once weekly until 100 days post-transplant.
  - Electrolytes, glucose, creatinine, BUN, every day as inpatient. At the ambulatory clinic, electrolytes are monitored a minimum of once per week.
  - Ca++, Mg++, PO4, albumin, twice a week as inpatient. At the ambulatory clinic, they are monitored a minimum of once per week
  - Bilirubin [total/direct], AST, alkaline phosphatase, LDH, a minimum of two times a week as inpatient. At the ambulatory clinic, monitoring is as follows: – If LFT's elevated: twice weekly.
  - INR is monitored weekly for patients on prophylactic Warfarin.
  - Blood cultures (aerobic and anaerobic) are obtained from patients receiving > 0.5 mg/kg/day of prednisone or prednisone equivalent. Twice weekly when inpatient.

## 9.2 Infusion Response Assessment

**Bioanalytical PK method:** This assay will be performed by Vir Biotechnology. A validated Electrochemiluminescence (ECL) Immunoassay is used to quantify sotrovimab in human serum samples. AbD34205 mu IgG2a (an anti-LS monoclonal antibody against the Fc region of VIR-7831) is coated onto an MSD High Bind plate (ECL capable). Sotrovimab in standards, QC's, controls and samples is captured onto the coated plate. After thorough washing of the wells to remove the unbound drug, Ruthenylated AbD42688 rFab is added to the wells. The conjugate binds to the captured sotrovimab. Following the incubation of the detection reagent, the plate is washed followed by addition of freshly prepared 1% formaldehyde for fixation and MSD read buffer. The assay plate is then read using an MSD ECL plate reader. Anti-drug antibodies may also be analyzed.

**Neutralization assay:** This assay may be performed at the Fred Hutch as an exploratory analysis using a SARS-CoV-2 pseudotyped virus assay as previously described(29). Briefly, this is a functional test to assess the ability of antibodies to bind and prevent infection of cultured cells with a pseudotyped virus that utilizes the spike protein of SARS-CoV-2 for infection and expressed luciferase. The endpoint neutralization titer of the serum will be determined as the dilution resulting in 50% neutralization ( $ID_{50}$ ).

**Binding antibodies (IgG):** This assay will be conducted at the Fred Hutch. We will use an indirect enzyme-linked immunosorbent assay (ELISA) or Luminex assay for quantification of anti-SARS-CoV-2 spike and nucleoprotein IgG and total IgG as previously described(30). Briefly, 96-well microtiter plates will be coated with recombinant SARS-CoV-2 spike or nucleoprotein or polyclonal goat anti-human IgG. Serum samples will be initially diluted at 1:100 and nasal samples will be diluted 1:10. Diluted specimens will be incubated in duplicate on the plate followed by addition of secondary goat anti-human IgG-horseradish peroxidase (HRP). Optical densities (OD) will be measured with a spectrophotometer. Plates will include a positive control monoclonal antibody against SARS-CoV-2 spike. If available, donor serum may also be analyzed using an ELISA assay for SARS-CoV-2 spike and nucleocapsid protein to ascertain SARS-CoV-2 infection and vaccination status.

**SARS-CoV-2 PCR:** This assay will be performed by UW Virology. We will use the FDA-authorized Panther Fusion SARS-CoV-2 real-time RT-PCR assay to detect SARS-CoV-2 in nasal swabs. The limit of detection of this assay is 0.01 TCID50/mL. The assay is a qualitative assay so does not have a lower limit of quantitation but does yield Ct values which will be recorded. The current standard practice for post-transplant care is to also obtain weekly surveillance PCR testing in allogeneic transplant patients prior to conditioning to day +100 post-transplant and also in autologous transplant patients prior to conditioning to day +30 post-transplant. These results will be obtained by review of electronic medical records. If the standard practice changes such that weekly surveillance swabs are no longer performed, we may provide additional swabs to participants for weekly PCR surveillance. A second foam swab will be performed as needed based on symptoms to test for acute SARS-CoV-2 infection. If positive for SARS-CoV-2, weekly nasal swabs will be obtained longitudinally for SARS-CoV-2 PCR until negative or until week 36. If breakthrough infection does occur, we will sequence the spike gene (or entire viral genome) to determine the variant and identify possible resistance mutations.

## 10. ADVERSE EVENT REPORTING

### 10.1 Definition of Adverse Events

**Adverse Event:** The International Council for Harmonization (ICH) guideline E6(R2) defines an AE as any untoward medical occurrence in a patient or clinical investigation subject administered a pharmaceutical product regardless of its causal relationship to the study treatment. An AE can therefore be any unfavorable and unintended sign (including an abnormal laboratory finding), symptom, or disease temporally related to the use of medicinal (investigational) product. The occurrence of an AE may come to the attention of study personnel during study visits and interviews or by a mAb recipient presenting for medical care.

AEs must be graded by the Principal Investigator or an authorized designee for severity and relationship to study product (see below). Severity can be assessed by a licensed clinician (i.e., physician, nurse, nurse practitioner, physician's assistant). Relationship to study product can only be assessed by a clinician licensed to make medical diagnoses (i.e., physician, nurse practitioner, physician's assistant) listed on the Form FDA 1572.

**Serious Adverse Event:** An SAE is defined as an AE meeting one of the following conditions:

- Results in death during the period of protocol-defined surveillance, except deaths that are the result of trauma or accident or the primary underlying malignancy.
- Is life-threatening (defined as a subject at immediate risk of death at the time of the event).
- Requires inpatient hospitalization or prolongation of existing hospitalization beyond the expected length of stay and during the period of protocol-defined surveillance. Hospitalizations for scheduled treatments, including scheduled admission for HCT are not SAE by these criteria.
- Results in a persistent or significant disability/incapacity.
- A congenital anomaly/birth defect.
- Any other important medical event that may not result in death, be life threatening, or require hospitalization, may be considered an SAE when, based upon appropriate medical judgment, the event may jeopardize the subject and may require medical or surgical intervention to prevent one of the outcomes listed above. Examples of such medical events include allergic bronchospasm requiring intensive treatment in an emergency room or at home, blood dyscrasias or convulsions that do not result in inpatient hospitalization, or the development of drug dependency or drug abuse.

**Unexpected Adverse Event:** An unexpected adverse event is defined as an event that has a nature or severity, or frequency that is not consistent with the applicable investigator brochure, or the prior medical condition of the subject or other treatment given to the subject. “Unexpected,” as used in this definition, refers to an adverse drug experience that has not been previously observed and reported in preclinical or clinical studies rather than an experience that has not been anticipated based on the pharmacological properties of the study drug.

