## 10.3 Relationship to the Study Infusion

Association or relatedness to the study agent will be assessed by the investigator as follows:

- Definite: The event follows a reasonable temporal sequence from exposure to the investigational agent, has been previously described in association with the investigational agent, and cannot reasonably be attributed to other factors such as the subject's clinical state, other therapeutic interventions or concomitant medications; AND the event disappears or improves with withdrawal of the investigational agent and/or re-appears on re-exposure (e.g., in the event of an infusion reaction).
- Probable: The event follows a reasonable temporal sequence from exposure to the investigational agent and has been previously been described in association with the investigational agent OR cannot reasonably be attributed to other factors such as the subject's clinical state, other therapeutic interventions, or concomitant medications.
- Possible: The event follows a reasonable temporal sequence from exposure to the investigational agent, but could be attributable to other factors such as the subject's clinical state, other therapeutic interventions or concomitant medications.
- Unlikely: Toxicity is doubtfully related to the investigational agent(s). The event may be attributable to other factors such as the subject's clinical state, other therapeutic interventions, or concomitant medications.
- Unrelated: The event is clearly related to other factors such as the subject's clinical state, other therapeutic interventions, or concomitant medications.

For general AE assessment, an AE is considered related if it is assessed as definitely, probably, or possibly related; unrelated if it is assessed as unlikely related or unrelated.

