#### **Reporting to FDA**

- SAEs related to the study drug that are unexpected, and fatal or life-threatening will be reported to the FDA no later than 7 calendar days after SAE awareness.
- SAEs related to the study drug that are unexpected and serious (not fatal or life-threatening) are to be reported to the FDA no later than 15 calendar days after SAE awareness.
- All other SAEs will be submitted with the FDA Annual Report in summary form.

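### Section 10.1 holds two tests of 'unexpected' that can disagree, so a suspected reaction new to VIR-7831 that resembles a transplant complication could miss the 7- or 15-day FDA report

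*Combined protocol and SAP*

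**What the plan says.** The protocol defines an unexpected adverse event in section 10.1, in two sentences. The first compares the event with three things. It is unexpected if its kind, severity or frequency is "not consistent with the applicable investigator brochure, or the prior medical condition of the subject or other treatment given to the subject". The second says that the term "refers to an adverse drug experience that has not been previously observed and reported in preclinical or clinical studies", as distinct from one not anticipated from the drug's pharmacology.

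Section 10.4.1 then uses the term as a gate. An IND safety report is due only for an event that is serious, related and unexpected. Under its heading on reporting to the FDA, related SAEs "that are unexpected, and fatal or life-threatening will be reported to the FDA no later than 7 calendar days" after awareness, and those that are "unexpected and serious (not fatal or life-threatening) are to be reported to the FDA no later than 15 calendar days". The remainder follow a default rule: "All other SAEs will be submitted with the FDA Annual Report in summary form".

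For attribution in IND reporting, section 10.4.1 uses the suspected-adverse-reaction definition of 21 CFR 312.32, which asks for evidence suggesting a causal link. It does not expressly take a definition of expectedness from that regulation. Section 10.1 is therefore the only place where the protocol writes that test down.

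**The concern.** The first sentence places the subject's illness and other treatment beside the brochure as grounds for calling an event consistent, and so expected. In this trial that background is broad. Every subject is infused 1 to 7 days before conditioning (section 6.1), so SAEs after the infusion will overlap in time with conditioning and transplant toxicity. Section 7 also states that there are no PK or immunogenicity data for 2,000 mg IV, the dose planned for the remaining 30 subjects.

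At stake is how quickly the FDA hears of a suspected reaction not previously described for the drug. If its resemblance to a transplant complication makes it expected, it goes to the annual summary. Patient background would then have decided the reporting route after the causality step had already allowed that the drug may be responsible.

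**Working it through.** There is no planned figure to reproduce. The check is a comparison of wording, a count of cases, and one ratio.

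**1. The two sentences side by side.** The first sentence has three reference points: the brochure, the prior condition and other treatment. The second has one, earlier experience with the drug. Neither withdraws the other.

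**2. Count of cases.** An event either fits or does not fit each of the three reference points, which gives 2 × 2 × 2 = 8 combinations. The first sentence can be read in two ways: (a) unexpected only if the event fits none of the three, which is the ordinary reading, or (b) unexpected if it fails to fit at least one. Column (c) is a brochure-only test. The second sentence corresponds to (c) if the brochure records what has been observed with the drug, which is an assumption.

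| Fits brochure | Fits prior condition | Fits other treatment | (a) | (b) | (c) |
|---|---|---|---|---|---|
| yes | yes | yes | – | – | – |
| yes | yes | no | – | unexpected | – |
| yes | no | yes | – | unexpected | – |
| yes | no | no | – | unexpected | – |
| no | yes | yes | – | unexpected | unexpected |
| no | yes | no | – | unexpected | unexpected |
| no | no | yes | – | unexpected | unexpected |
| no | no | no | unexpected | unexpected | unexpected |
| **Total** | | | **1 of 8** | **7 of 8** | **4 of 8** |

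Under (a), 3 of the 4 combinations that do not fit the brochure become expected only because of patient background. Under (b) the gap closes, but 3 of the 4 combinations that do fit the brochure become unexpected, so a reaction already described for the drug would count as unexpected merely because it does not fit the subject's illness. These are counts of logical cases, not probabilities.

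**3. One event traced through the rules.** Take a fatal SAE that meets the attribution test of section 10.4.1, has not been reported with VIR-7831, and is of a kind also seen with conditioning.
- By the second sentence of section 10.1 it is unexpected and goes to the FDA within 7 days.
- By the first sentence, reading (a), it fits other treatment given and is expected. It fails both expedited rules and falls to the annual summary.

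A non-fatal, non-life-threatening SAE takes the same two paths, with 15 days in place of 7.

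**4. Size of the delay.** The protocol gives no date for the annual report. Assuming a wait of up to 365 days, the ratios are 365 / 7 = 52 and 365 / 15 = 24. Both are upper bounds, because an SAE shortly before an annual report would wait far less.

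**The case against.** The strongest reply is that the second sentence tells the reader how to understand the first. It refers to "an adverse drug experience that has not been previously observed and reported in preclinical or clinical studies", so an event never seen with VIR-7831 is unexpected and is expedited. Reading (b) also leaves no gap, and section 10.4.1 commits IND reporting to 21 CFR 312.32 generally. These are fair points, and they show that a reader can reach the right route. They do not make the text settle it: the background clauses remain, both readings are available, and the only definition expressly taken from the regulation concerns attribution. The documents do not reproduce the regulation's own meaning of unexpected, so nothing is concluded from it here.

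A reader might infer more than the documents support, in four ways.

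- **That events graded 'Possible' will usually be filtered out.** Section 10.3 describes these as events that "could be attributable to other factors such as the subject's clinical state, other therapeutic interventions or concomitant medications", and counts them as related. That grouping is stated to be for general AE assessment. FDA reporting has its own attribution test in section 10.4.1, and an event that fails it goes to the annual summary whatever section 10.1 says.
- **That different sites will decide differently.** Accrual is planned at one center, with another only if accrual is slow (section 12.3), and one sponsor-investigator holds responsibility for IND reporting.
- **That the 10-day IRB rule is affected in the same way.** IRB reporting follows IRB policy and turns on the investigator's opinion. It does not cite the section 10.1 definition.
- **That a new toxicity could go unseen for a year.** Every SAE goes to Vir/GSK within 24 hours whatever its cause, the drug sponsor cross-reports relevant events to the parent IND, and section 13.2 has SAEs reviewed as they occur and adverse events at least weekly.

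**Conclusion.** The point holds as a drafting defect with a practical consequence. The protocol's only written test of expectedness can be read in ways that give opposite FDA reporting routes for the same event. On the ordinary reading of its first sentence, a serious, causally suspected event that is new to VIR-7831 can miss the 7- or 15-day report because it resembles a conditioning or transplant complication.

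The consequence is possible delay or misrouting of FDA reports under this IND, not loss of the event. The 24- and 52-fold ratios are ceilings that rest on the assumed 365-day wait. How many SAEs would be affected cannot be derived from the documents, and a failure of expedited reporting has not been shown. The conclusion assumes that staff will apply section 10.1 as written, and that the event has already passed the attribution test of section 10.4.1. Sample size and analysis are not affected. An amendment is worthwhile because the change is small and removes the ambiguity.

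**What to change.** In the first sentence of the definition in section 10.1, end the comparison at the investigator brochure and delete the two clauses after it, on the subject's prior condition and on other treatment. State that, for the FDA rules in section 10.4.1, expectedness is judged only against the investigator brochure for VIR-7831. Weigh patient background in the causality assessment alone: the attribution test of section 10.4.1 for IND reporting, and section 10.3 for general AE assessment. Leave the IRB rule as it is.

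The cost is a wording amendment and probably a few more expedited reports, limited to SAEs already judged to be suspected adverse reactions. Dose, schedule, sample size and analysis do not change.
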